5.1.2. Additional considerations

Demographic characteristics will also be summarized on Enrolled Set for web public disclosure.

Subject disposition will be summarized by group using descriptive statistics:

- Number of subjects screened, randomised, vaccinated and withdrawn including withdrawal reasons in each group and overall will be tabulated.

Vital signs will be summarized by group using descriptive statistics at all timepoint(s) the information is collected on Exposed Set and Per-protocol Set.

Summary of important protocol deviations leading to elimination will be tabulated by group. An individual listing will also be provided.

Summary of medical history will be performed on Exposed Set by Medical Dictionary for Regulatory Activities (MedDRA) and preferred term.

Summary of vaccination history will be performed on Exposed Set by using GSKDRUG dictionary.

Additional analyses by country and/or by site may be performed if deemed necessary

5.2. Immunogenicity

5.2.1. Analysis of immunogenicity planned in the protocol (Amended 03-DEC-2020)

The primary analysis on immunogenicity will be based on the Per Protocol set. If, in any study group and at any timepoint, the percentage of enrolled or vaccinated subjects with serological results excluded from the Per Protocol set for analysis of immunogenicity is 5% or more, a second analysis based on the Exposed Analysis Set will be performed to complement the Per Protocol analysis.

Endpoint	Statistical Analysis Methods
Primary	
(US + ex-US data to be pooled for the first vaccination)
 
For each group, at each time point that blood samples are collected for humoral immune response and for each assay (unless otherwise specified):
 
 • GMCs/GMTs and their 95% CI will be tabulated and represented graphically pooled. • Geometric mean of ratios of antibody titer/concentrations at each individual post-vaccination time point over pre-vaccination (screening) will be tabulated with 95% CI pooled. • Antibody titer/concentration will be displayed using reverse cumulative curves pooled. • The kinetics of GMT/GMCs will be plotted as a function of time for subjects with results available at all time points pooled. • The GMT/GMCs ratio and their 90% CI between RSVPreF3 dTpa and RSVPreF3 alone in terms of RSV-A Nab titers and RSV IgG antibody concentrations may be calculated at Screening, and/or Day 8, and/or Day 31 post 1st vaccination pooled for all subjects. • A further exploratory between-groups analysis will be performed at Day 8 or Day 31 using an ANCOVA model by including study groups, study formulation (US and ex-US), age category, and level of antibodies at Screening as covariates.
Secondary	
(US and ex-US data to be considered pooled, then separately for the first vaccination)
 
For each group, at each time point that blood samples are collected for humoral immune response and for each assay (unless otherwise specified):
 
 • GMCs/GMTs and their 95% CI will be tabulated and represented graphically by formulation (US and ex-US) Geometric mean of ratios of antibody titer/concentrations at each individual post-vaccination time point over pre-vaccination (screening) will be tabulated with 95% CI by formulation (US and ex-US). • Antibody titer/concentration will be displayed using reverse cumulative curves by formulation (US and ex-US). • The kinetics of GMT/GMCs will be plotted as a function of time for subjects with results available at all time points by formulation (US and ex-US). • Booster response rates for PT, FHA and PRN (with exact 95% CI) will be calculated by group for each formulation (US and ex-US). 
For the data collected for the second vaccination, the humoral immune response of RSV PreF3 will be summarized based on 2 dose level (60 and 120 µg) from the first vaccination.

Endpoint	Statistical Analysis Methods
	
 • GMCs/GMTs and their 95% CI will be tabulated and represented graphically for prior and post 2nd dose vaccination • Geometric mean of ratios of antibody titer/concentrations at individual post- 2nd dose vaccination time point (visit 6) over prior 2nd dose vaccination time point (visit 4) will be tabulated with 95% CI • Antibody titer/concentration will be displayed using reverse cumulative curves on prior and post 2nd vaccination • The kinetics of GMT/GMCs will be plotted as a function of time for subjects with results available at all time points including the visits from the first vaccination. 
Booster responses to PT, FHA and PRN antigens are defined as:
 
 • For subjects with pre-vaccination antibody concentration below the assay cut-offs: post-vaccination antibody concentration \geq 4 times the assay cut-offs, • For subjects with pre-vaccination antibody concentration between the assay cut-offs and below 4 times the assay cut-offs: post-vaccination antibody concentration \geq 4 times the pre-vaccination antibody concentration, and • For subjects with pre-vaccination antibody concentration \geq 4 times the assay cut-offs: post-vaccination antibody concentration \geq 2 times the pre-vaccination antibody concentration. 
 – The percentage of subjects with anti-D antibody concentrations \geq 1.0 IU/mL by ELISA and the percentage of subjects with anti-T antibody concentrations \geq 1.0 IU/mL by ELISA (with exact 95% CI) will be calculated by group for each formulation (US and ex-US). – The GMT/GMCs ratio and their 90% CI between RSVPreF3 dTpa and dTpa placebo in terms of anti-PT, anti-FHA, anti-PRN, anti-D, anti-T will be calculated at Screening and Day 31 pooled for all subjects and by formulation (US and ex-US). – A further exploratory between-groups analysis will be performed at Day 31 using an ANCOVA model by including study groups, study formulation (US and ex-US), age category, and level of antibodies at Screening as covariates. – For Boostrix booster response to antigens PT, FHA and PRN, the two-sided standardized asymptotic 95% CI for the group differences in the percentage of subjects with a booster response to each antigen in the RSVPreF3 dTpa vaccine group and (minus) the dTpa Placebo vaccine group on Day 31 post vaccination will be calculated for each formulation. – For Boostrix seroprotection rate (percentage of subjects with antibody concentrations \geq 0.1 IU/ml by ELISA) for antigens D and T, the two-sided standardized asymptotic 95% CI for the group differences in the percentage of subjects with antibody concentrations \geq 0.1 IU/ml in the RSVPreF3 dTpa vaccine group and (minus) the dTpa Placebo vaccine group at Day 31 post vaccination will be calculated for each formulation.
Tertiary	Will be described in a Statistical Analysis Plan finalised before database unblinding/freezing.

*The statistical method will not be applied to primary endpoint. For detailed rationale, refer to Section 8.

**pooled group definition is detailed in [Table 2](#)

5.2.2. Additional considerations

5.2.2.1. Between group analysis

The Non-inferiority on RSV-A neutralizing antibody titers at 31 days post 1st vaccination in the co-administration of RSVPreF3 vaccine + *Boostrix* compared to RSV+ Placebo will be evaluated based on the criterion below:

- The criterion to evaluate non-inferiority with respect to RSV-A neutralizing antibody titers is that the upper limits of the 95% CI on the GMT ratio (RSVPreF3 +*Placebo* divided by RSVPre3 + *Boostrix*) is less than or equal to 1.5 at 31 days post vaccination.

Following model will be applied to RSVPreF3 IgG antibody concentrations and RSV-A neutralizing antibody titers.

For the analysis of subjects at visit 3 (Day 31), the model will be explored and fitted via the proc glm procedure according to the following code:

```
PROC glm data=sero;
  CLASS group;
  MODEL log_val = baseline group age_cat country_US country_BE
  Output out= pred;
  LSMEANS group/pdiff cl alpha=0.1;
  RUN;
```

where **log_val** represents the log-transformed antibody value of the immunogenicity variable at a given post baseline timepoint (Day 8) or (Day 31), **baseline** is pre-vaccination logarithm10 transformation of the concentrations/titers, **group** indicates the study group, pooled groups (US and ex-US) will be considered in model then separate by formulation. **age_cat** is indicator variable (0/1) and will be treated as continuous in the model, **age_cat** equals 0 if the age category at vaccination between 18 - 32 years, otherwise **age_cat** equals 1 if age category is between 33 - 45 years at vaccination.

Country_US is indicator variable (0/1) and will be treated as continuous in the model, if subject from US, then variable will equal to 1, otherwise equals to 0, **Country_BE** is indicator variable (0/1) and will be treated as continuous in model, if subject from BE, then variable equals to 1, otherwise equals to 0, if subject is from Canada, above two indicators equal to 0. The inclusion of age category at vaccination, in the model depends on the availability of the variable and the necessity, therefore, the above SAS code serves as a reference and may be adjusted according to the analysis needs.

When considering group as separated by *Boostrix* formulation, remove **Country_US** and **Country_BE** from model.

GMT/GMC ratios between vaccine groups obtained using above model will be calculated by exponentiating mean difference of logarithm- transformed titres. The 90% CI and 95% CI for GMT/GMC ratio will be obtained by exponential-transformation of the CI for the group least square mean of the log-transformed titres/concentration from the above model.

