## 5. STUDY DESIGN

### 5.1. Scientific rationale for study design

This study is part of a clinical development plan of the RSVPreF3 vaccine for the protection of infants from RSV LRTI through maternal immunisation. This study will evaluate the safety and immunogenicity of the RSVPreF3 vaccine when it is co-administered with *Boostrix* in healthy non-pregnant women aged 18 to 45 years old. Two dose levels of RSVPreF3 will be evaluated in order to optimally select the dose level for further development. Two formulations of *Boostrix*, one containing 300 micrograms (dTpa\_300) and the other containing 500 micrograms (dTpa\_500) of aluminum are licensed in the US and outside the US (ex-US), respectively. The difference between the two formulations being the level of aluminium adjuvant. Both formulations will be studied.

Approximately 500 women will be randomised to 5 equal study groups corresponding to the two dose levels of RSVPreF3 given with and without co-administration of *Boostrix* and a comparator group receiving *Boostrix* plus a placebo. To facilitate decision making in the clinical development plan the primary analysis will take place at day 31. The primary objectives compare the safety and the immune response to RSVPreF3, 31 days after vaccination in the five pooled study groups. The sample size of 100 subjects per group in the combined formulations is planned to provide reasonable confidence to evaluate the AE rate and quantify immunogenicity interference. If an AE is not observed in a given treatment group, then this sample size provides at least 95% confidence to rule out an AE rate greater than 3.6% and there will be at least 90% power to claim non-inferiority with a margin of 1.5 between RSVPreF3 alone and RSVPreF3 in co-administration with *Boostrix*.

By enrolling approximately half the subjects in the US and half outside the US, as secondary objectives the effect of co-administration of RSVPreF3 data will be collected on both commercial *Boostrix* formulations. While secondary analyses will be described by formulation, differences between the US and ex-US formulations could be explained by ethnic and environmental differences. Specified secondary endpoints will be described pooled across all subjects or by formulation.

[figure not shown]

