## **9.2. Discontinuation of study vaccine(s)**

‘Discontinuation’ of study intervention refers to any participant who has not received all planned doses of study intervention. A participant who discontinued study intervention may continue other study procedures (e.g. safety or immunogenicity), planned in the study protocol at the discretion of the investigator.

The primary reason for premature discontinuation of the study intervention will be documented on the eCRF as follows:

- Adverse event requiring expedited reporting to GSK
- Unsolicited non-serious adverse event
- Solicited adverse event
- Not willing to be vaccinated
- Other (specify).

**CONFIDENTIAL**209141 (RSV MAT-011)  
Protocol Amendment 6 Final**9.3. Lost to follow-up**

A subject will be considered lost to follow-up if she repeatedly fails to return for scheduled visits and is unable to be contacted by the study site.

The following actions must be taken if a subject fails to return to the clinic for a required study visit:

- The site must attempt to contact the subject and reschedule the missed visit as soon as possible and counsel the subject on the importance of maintaining the assigned visit schedule and ascertain whether or not the subject wishes to and/or should continue in the study.
- Before a subject is deemed lost to follow-up, the investigator or designee must make every effort to regain contact with the subject (where possible, 3 telephone calls and, if necessary, a certified letter to the subject's last known mailing address or local equivalent methods). These contact attempts should be documented in the subject's medical record.
- Should the subject continue to be unreachable, he/she will be considered to have withdrawn from the study with a primary reason of lost to follow-up.

**10. STATISTICAL CONSIDERATIONS****10.1. Sample size determination****10.1.1. Hypotheses related to primary and secondary objectives**

No hypothesis driven sample size calculation was conducted due to the descriptive nature of the study.

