If a SD of log10 transformed RSV-A Nab of 0.4 is assumed, when the sample size is 50 subjects per group, the half width of the 90% CI on the log ratio of GMT between co-administration with dTpa and RSVPreF3 alone is 0.133. With an observed GMT ratio of 1, its 90% CI will be (0.74, 1.36). With subjects in US and ex-US combined, there will be at least 90% chance that the upper bound of one-sided 95% CI for the ratio of GMT of RSV-A Nab titer between RSVPreF3 alone and co-administration with dTpa is under 1.5-fold.

**Table 19      Precision and power in terms of RSV-A neutralizing antibody titers with a sample size of 100 subjects per group and 50 subjects per group**

Number of subjects per group	Ratio of GMT between two groups	SD*	90% CI		Power for non-inferiority test (%) ***
			LL	UL	
50	0.9	0.3	0.71	1.13	97.9
50	0.9	0.4	0.66	1.22	86.6
50	0.9	0.5	0.61	1.32	71.2
50	1.0	0.3	0.79	1.26	89.8
50	1.0	0.4	0.74	1.36	70.5
50	1.0	0.5	0.68	1.47	54.1
50	1.1	0.3	0.87	1.38	72.0
50	1.1	0.4	0.81	1.49	51.0
50	1.1	0.5	0.75	1.61	37.9
100	0.9	0.3	0.77	1.06	100
100	0.9	0.4	0.73	1.11	98.8
100	0.9	0.5	0.69	1.18	93.1
100	1.0	0.3	0.85	1.17	99.4
100	1.0	0.4	0.81	1.24	92.7
100	1.0	0.5	0.76	1.31	79.8
100	1.1	0.3	0.94	1.29	93.5
100	1.1	0.4	0.89	1.36	76.6
100	1.1	0.5	0.84	1.44	60.0

\*Standard deviation of log10 of RSV-A Nab titer. The highest standard deviation observed 30 days after vaccination in a previous GSK RSV study was 0.4.

\*\*Precision estimation for log GMT ratio using PASS 12.0.2 (CI for two means), LL: Lower Limit, UL: Upper Limit

\*\*\*PASS: Non-Inferiority Tests for Two Means using Differences with one-sided alpha 5% and Non-Inferiority Margin 0.176 on log 10 scale (corresponding to Non-Inferiority Margin 1.5 for GMT ratio).

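### The protocol's power of at least 90% for RSV-A non-inferiority is for the 90% CI limit; the SAP's criterion uses the 95% CI limit, which gives about 87% in the same scenario

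*SAP*

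**What the plan says.** Protocol 5.1 says that with 100 per group "there will be at least 90% power to claim non-inferiority with a margin of 1.5" between RSVPreF3 alone and RSVPreF3 with Boostrix. Section 10.1.2 repeats this for US and ex-US combined: "there will be at least 90% chance that the upper bound of one-sided 95% CI for the ratio of GMT" is below 1.5-fold. The footnote to Table 19 gives the basis as "Non-Inferiority Tests for Two Means using Differences with one-sided alpha 5% and Non-Inferiority Margin 0.176 on log 10 scale", and the table prints 90% CIs. It also explains the choice of SD: "The highest standard deviation observed 30 days after vaccination in a previous GSK RSV study was 0.4". Section 10.1.1 nevertheless states "No hypothesis driven sample size calculation was conducted due to the descriptive nature of the study". Protocol 10.3.3 sets no pass/fail rule; it says only that GMT ratios with 90% CIs may be calculated.

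The rule is in SAP Amendment 4, section 5.2.2.1. The criterion with "respect to RSV-A neutralizing antibody titers is that the upper limits of the 95% CI on the GMT ratio" (RSVPreF3 plus placebo over RSVPreF3 plus Boostrix) is a value of at most 1.5 at Day 31. The model code below it contains "LSMEANS group/pdiff cl alpha=0.1", with the remark that "the above SAS code serves as a reference and may be adjusted according to the analysis needs". The same section and SAP section 8 say that both a 90% and a 95% CI from the ANCOVA will be produced.

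**The concern.** The stated power and the decision rule refer to different confidence limits. A one-sided 5% test passes when the upper limit of a two-sided 90% CI is below the margin. A rule on the upper limit of a two-sided 95% CI is a one-sided 2.5% test, which is harder to pass with the same data. The protocol writes one-sided when it means one-sided; the SAP criterion does not. The SAP also lists a 95% CI alongside the 90% CI, and if its 95% limit were one-sided it would coincide with the 90% CI limit already reported. The natural reading is therefore two-sided 95%. The sample code, with alpha at 0.1, prints 90% limits and so does not produce the limit the criterion needs.

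This is the only pass/fail threshold for an immunogenicity comparison in the plan. A reader who takes the protocol's power at face value would overstate the chance of meeting it. A result that falls between the two limits could be reported either way.

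**Working it through.** **Inputs.** All are from protocol 10.1.2 and Table 19 unless noted.
- Margin: 0.176 on log10 (1.5-fold).
- SD of log10 titre: 0.4 (the table covers 0.3 to 0.5).
- True ratio: 1.
- n: 100 per group per dose level, formulations combined.
- Attrition: 5%, about 475 of 500 (protocol 5.3), so 475/5 = 95 per group. This assumes that all of them are in the Day 31 per-protocol set.

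**Formula.** Two-sample t-test with df = 2n − 2:
- SE = SD × √(2/n)
- noncentrality = (0.176 − log10 ratio)/SE
- power = probability that a noncentral t exceeds the one-sided critical value

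**Reproducing the protocol.** At n = 100, SE = 0.4 × √0.02 = 0.0566 and the noncentrality is 0.176/0.0566 = 3.11. At one-sided 5% the critical value is 1.653 and power is **92.7%**; Table 19 gives 92.7. All 18 powers in Table 19 reproduce on this basis to within 0.1 point, so its basis is not in doubt.

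**The SAP rule.** With the same inputs at one-sided 2.5%, the critical value is 1.972 and power is **87.2%**. At n = 95, SE is 0.0580 and the noncentrality is 3.03; power is 91.6% at one-sided 5% and **85.5%** at 2.5%. The SAP rule first reaches 90% at 110 per group.

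**Other scenarios at n = 100** (Table 19 power, then power under the SAP rule, %):

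| True ratio | SD 0.3 | SD 0.4 | SD 0.5 |
|---|---|---|---|
| 0.9 | 100 / 99.9 | 98.8 / 97.4 | 93.1 / 87.7 |
| 1.0 | 99.4 / 98.5 | 92.7 / 87.2 | 79.8 / 69.7 |
| 1.1 | 93.5 / 88.4 | 76.6 / 65.8 | 60.0 / 47.4 |

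**Where the rules disagree.** The largest observed ratio that passes is 10^(log10 1.5 − t × SE).
- n = 100: 10^(0.1761 − 0.0935) = 1.21 under the protocol's test, and 10^(0.1761 − 0.1116) = 1.16 under the SAP rule.
- n = 95: 1.20 and 1.15.

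The chance of landing between the two limits at n = 100 is 92.7 − 87.2 = 5.5% at true ratio 1, and 76.6 − 65.8 = 10.8% at 1.1.

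**Baseline adjustment.** The SAP rule regains 90% if the residual SD is at most 0.382 (n = 100) or 0.372 (n = 95). If adjustment works through the baseline titre alone, the correlation needed is √(1 − (0.382/0.4)²) ≈ 0.30, or √(1 − (0.372/0.4)²) ≈ 0.37. The documents give no correlation. Over an assumed range of 0 to 0.6, power at n = 100 runs from 87.2% to 97.2%.

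**Dose-pooled groups.** With 200 per group, power is 99.7% at one-sided 5% and 99.2% at one-sided 2.5%.

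**The case against.** No printed figure is wrong. Table 19 is correct and states its alpha, and it already shows powers down to 60.0% at n = 100. The 87.2% is unadjusted, whereas SAP section 8 drops the unadjusted ratio in favour of an ANCOVA, and a modest baseline correlation would restore 90%. The criterion names no dose, and SAP Table 2 defines dose-pooled groups for which power is about 99% under either limit. Sidedness is not explicit either: the code's alpha of 0.1 fits a one-sided 95% bound, in which case the documents agree and only a word is missing. The comparisons are descriptive, the stricter limit is conservative, and both intervals will be reported.

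Much of this stands, and it limits the consequences. It does not remove the mismatch. The protocol's claim is itself unadjusted, and the plan neither states a baseline correlation nor claims a gain from adjustment. The protocol powers 100 per group, which is the per-dose comparison. The separately listed 90% and 95% CIs make the two-sided reading the natural one. Reporting both intervals does not say which one settles the non-inferiority statement.

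**Conclusion.** The point holds. The claim of at least 90% belongs to a one-sided 5% test that the SAP's criterion does not use. In the protocol's own scenario, the written criterion has about 87% power at 100 per group and about 85.5% at 95. This rests on reading the SAP's 95% CI as two-sided, on the per-dose comparison, on SD 0.4 (the highest value the protocol cites) with a true ratio of 1, and on no gain from covariates. At SD 0.3 with a ratio of 1, the SAP rule still has 98.5%. If the dose-pooled groups were meant, the shortfall disappears. Type I error is not inflated. This should be fixed as an inconsistency between a stated power and a decision rule in a study labelled descriptive.

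**What to change.** Keep the SAP's stricter limit. In SAP 5.2.2.1, state that the criterion is the upper limit of the two-sided 95% CI and that it applies to each RSVPreF3 dose level with formulations pooled, which is the comparison the protocol powers. Set alpha to 0.05 in the code for that output. In protocol 5.1 and 10.1.2, restate the unadjusted power as about 87% at 100 per group and about 85.5% at 95. In Table 19, either add the one-sided 2.5% powers shown above or label the existing column as one-sided 5% only.

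Moving the criterion to the 90% CI limit would also reconcile the documents, but it loosens the rule. It is acceptable only if documented as decided before the Day 31 analysis, when the statistician is unblinded (SAP 7.1.1).

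The cost is one sentence and one code option in the SAP, plus the power figures in the protocol. No participants are added, and the stated power falls by about 5 to 6 points.

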5.2.2.2. Percentage difference between two groups

The percentage difference of response rate in terms of antigen PT, FHA and PRN [Camargo, 1984; Melville, 1983], together with the two-sided standardized asymptotic 95% CI in the RSVPreF3 dTpa group (minus) the dTpa Placebo group on Day 31 will be provided.

The percentage difference of seroprotection rate in terms of antigen D and antigen T [Vidor, 2008] with the two-sided standardized asymptotic 95% CI for RSVPreF3 dTpa vaccine group and (minus) the dTpa Placebo vaccine group by formulation at Day 31 will be calculated.

